Methodology:	
Research design. The RTM Protocol effectiveness study implies a randomised field trial comparing RTM with treatment-as-usual (TF-CBT, EMDR or pharmacotherapy). It is chosen and will be standardised based on CONSORT 2010 Statement: reporting parallel group randomised trials. To enhance the external validity of the findings, all the interventions are planned to be explored among three different settings of mental health care accustomed to Ukraine: mental health hospital care (inpatient and outpatient care for veterans) and psychotherapeutic practice (for civil trauma survivors).
 
Measures. Primary outcome effectiveness measures are MH professional proved existence or loss of PTSD diagnosis and/or PTSD symptoms severity measured by PTSD Checklist PCL-5 (re-experiencing of trauma, avoidance of trauma-related stimulus, negative alterations in cognition and mood, hyper-arousal).
 
Among secondary outcome measures will be the existence and severity of depression and anxiety-related symptoms according to PHQ-9 and GAD-7 scales.
 
Data analysis. Descriptive Statistics: means, SDs, medians, frequencies and percentages, baseline comparability between groups (t-tests, chi-square tests). Primary and Secondary Outcome Analysis: mixed-effects repeated measures ANOVA. Handling Missing Data: multiple imputation or maximum likelihood estimation under MAR assumption. Effect Size Reporting: Cohen's d, odds ratios, and 95% confidence intervals.
 
Data collection will be in Ukrainian language (all the scales are validated in Ukrainian and recommended by the World Health Organisation for the screening of the mentioned mental health conditions) at baseline (diagnostic session), 1 month after complete treatment application, in 6 months (follow-up booster session), and in 12 months (second follow-up booster session).

Study 2: The RTM Protocol and Training Feasibility Study

Target sample size: (Please justify the target sample size, either statistically or by referring to existing literature)	
The research sample for the FEASIBILITY STUDY is expected to be 20 participants according to the trauma-related cases/workforce availability ratio of implementing partners: 10 persons from each site.
 
The number of clients is expected to be 60 persons (persons treated with the RTM Protocol) according to the RTM Protocol effectiveness study description.

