
Are there any specific risks to the human participants involved, if any.
	
Risk of adverse effects is usually considered in studies on mental health interventions. It is important to mention that possible adverse effects are minimised by the RTM Protocol procedure itself, which is focused on processing traumatic events without triggering emotional hyperarousal by quick termination of every therapeutic technique at first sign of client' distress.
 
Nevertheless, clients' support will be organised according to existing procedures and requirements of mental health care established by the implementing partners (RCFG, NPA) and through adverse-effect management and reporting that aligns with safety requirements of the CONSORT-Harms 2022 framework.
 
Adverse-effect management includes the following measures:
 
 - anticipating adverse effects (PTSD symptoms deterioration; emotional distress); - adverse effects monitoring & detection (using implemented into the Protocol assessments procedures as measurement of subjective distress and physiological arousal calibration, as

	
well as additional monitoring with the PCL-5 (for PTSD), PHQ-9 (for depression), and GAD-7 (for anxiety) diagnostic scales;
 
- mitigating adverse effects (terminating the intervention, utilizing grounding and "break state" techniques, referring for other types of help and support, providing extra visits, crisis referrals, and medication);
 
- recording every episode of adverse effects in patient documentation;
 
- reporting adverse effects to the site coordinator for processing and reflection in study reports and publications.
 
No mentioned project activities will be executed in Luxembourg or with Luxembourg or EU residents.

--	--

Study 2: The RTM Protocol and Training Feasibility Study

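### In-treatment detection of adverse effects is stated only through readings that belong to RTM, so recorded distress is likely to be higher on RTM at equal true rates

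*Protocol*

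**What the plan says.** Study 1 is "a randomised field trial comparing RTM with treatment-as-usual (TF-CBT, EMDR or pharmacotherapy" (Protocol, Section 4, Study 1, Methodology). Section 6 plans three RTM and three control groups of 20, so 60 per arm.

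The safety text is in Section 5, Study 1, in the row on specific risks. It says that "possible adverse effects are minimised by the RTM Protocol procedure itself" and promises "adverse-effect management and reporting that aligns with safety requirements of the CONSORT-Harms 2022 framework". A list of measures follows:

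- Effects expected: "anticipating adverse effects (PTSD symptoms deterioration; emotional distress".
- Detection, first route: "using implemented into the Protocol assessments procedures as measurement of subjective distress and physiological arousal calibration".
- Detection, second route: the shared scales, as "well as additional monitoring with the PCL-5 (for PTSD), PHQ-9 (for depression), and GAD-7 (for anxiety) diagnostic scales".
- Recording of each adverse-effect episode in the patient's documentation.
- Onward use: "reporting adverse effects to the site coordinator for processing and reflection in study reports and publications".

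The list gives no times for the scales. The only schedule is the general one in Section 4: "at baseline (diagnostic session), 1 month after complete treatment application, in 6 months (follow-up booster session", and again at 12 months. Section 6 gives 2 weeks instead of 1 month for the first follow-up. Either way, every assessment after baseline falls after treatment has ended.

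**The concern.** The two detection routes differ in whom they cover and when. The session readings belong to one randomised treatment and operate during treatment. The scales cover both arms, but their stated schedule has no point during treatment. One of the two expected effects, emotional distress, is close to what the session readings measure. For the control treatments the protocol names no session reading, adverse-effect question or form.

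If recorded episodes are then set side by side by arm, the counts partly reflect how closely each arm was watched. RTM could look less safe than it is. Equally, a real excess on RTM could be dismissed as closer watching, and the data would not settle which is true. Analysis cannot repair this, because control episodes that nobody asked about cannot be recovered later.

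**Working it through.** **Which protocol is meant.** In the Section 5 row, the word could mean the study protocol or the RTM Protocol. The same row names the RTM Protocol procedure as what limits adverse effects, and the study procedures in Sections 4 and 6 contain no arousal calibration. The reading that fits is the RTM Protocol, the experimental treatment.

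**Routes by arm, as stated.**

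| Route | RTM | Usual treatment |
|---|---|---|
| Distress and arousal readings in session | stated | not stated |
| PCL-5, PHQ-9, GAD-7 at baseline and after treatment | stated | stated |
| Common adverse-effect log or question | not stated | not stated |

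**Illustration of direction and size.** The protocol gives no adverse-effect rate or detection probability, so there is no figure of its own to reproduce on this point. The sample-size calculation in Section 4 does not enter. The only document input is 60 per arm. The rest is assumed:

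- *p*: true proportion of participants with an event, equal in both arms;
- *s*: probability that the scales detect an event, equal in both arms, 40% to 80%;
- *r*: probability that the session readings detect it, 25% to 75% on RTM and 0 on control, because no such route is stated there;
- the two routes act independently.

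Expected detected events:

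- RTM: 60 × p × [1 − (1 − s)(1 − r)]
- Control: 60 × p × s
- Ratio: [1 − (1 − s)(1 − r)] / s = 1 + r(1 − s)/s, which does not depend on p.

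With p = 20% and s = 60%, control has 60 × 0.20 × 0.60 = 7.2 events. RTM has 8.4, 9.6 or 10.8 for r = 25%, 50% or 75%.

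Ratio of detected events, RTM to control, at equal true rates:

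| | r = 25% | r = 50% | r = 75% |
|---|---|---|---|
| s = 40% | 1.375 | 1.750 | 2.125 |
| s = 60% | 1.167 | 1.333 | 1.500 |
| s = 80% | 1.063 | 1.125 | 1.188 |

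**What follows.** The ratio grows as *s* falls. An effect that the post-treatment scales catch well, such as lasting PTSD worsening, is little affected. Distress that arises and settles during treatment, which those scales would often miss, is affected most. If the control arm has a session route of the same sensitivity (equal *r*), the ratio is 1.00 for every value tried.

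**The case against.** The case on the other side has real force, and several stronger readings that a reader might infer do not hold.

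- *Usual treatment has no in-session detection.* The protocol does not say this. It does not describe control sessions, and it places client support under the partners' existing procedures, without limiting that to RTM. Control-arm detection is unstated, not shown to be absent. An RTM excess in recorded events is therefore likely, not certain.
- *PTSD deterioration has no measure common to both arms.* It has one: PCL-5 is named as monitoring for PTSD, and the protocol schedules it without restriction by arm. Only a worsening amount is missing, and that alone could be left to an analysis plan.
- *Every reading becomes an adverse effect.* The protocol records episodes of adverse effects, not readings, and treats signs of distress as part of how a session is run. The gap is that no rule separates the two.
- *The excess can be put as a number of participants.* An assumed 2% to 5% chance per session over 3 to 5 sessions gives 1 − 0.98³ = 5.9% to 1 − 0.95⁵ = 22.6%, or 3.5 to 13.6 of 60. The protocol gives neither input, and the result is the yield of one route, not a difference between arms.

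It is also true that no between-arm harms analysis is written down, and that the primary and secondary outcomes are untouched. But the protocol sends adverse effects to publication and claims alignment with a harms-reporting framework, so a comparison by arm is a fair expectation. How harms are elicited has to be fixed in the protocol. What stands is that detection during treatment is written in for one arm and left to unstated local practice in the other.

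**Conclusion.** The point holds as a matter of unequal ascertainment. One of the two stated detection routes belongs to RTM, and it is the only one clearly placed during treatment. No counterpart is stated for usual treatment. Emotional-distress events are therefore likely to be recorded more often on RTM at equal true rates.

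The direction rests on two assumptions: that control sessions are not watched with equal sensitivity under local procedures, and that at least some readings lead to recorded events. The size cannot be derived from the documents. The ratios of about 1.1 to 2.1 show what the assumed detection probabilities imply and are not an estimate for this trial. The efficacy comparisons are not affected.

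**What to change.** In Section 5, Study 1:

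1. Set one definition of an adverse effect for both arms, with a rule that separates a routine session reading from an event.
2. Elicit it with the same short log, asked the same way at matched times during and after treatment in both arms. Scales taken only after treatment would miss the in-treatment distress that the protocol itself expects.
3. Pre-set one amount of worsening from baseline on each of PCL-5, PHQ-9 and GAD-7, applied equally to both arms.
4. Base any between-arm harms comparison on these shared sources. Report events found only through RTM session readings in full but separately, labelled as detectable on RTM only, so that they are neither hidden nor compared with a control arm that lacked the route.

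A shared log does not make detection perfectly equal, since RTM therapists will still have seen the readings when they complete it. Asking the same questions at the same times reduces the difference, and the separate label shows what remains.

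Clinical handling of distress is unchanged. The cost is some wording and one extra short form per contact in both arms; the three scales are already collected.

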The RTM Protocol and Training feasibility study will evaluate the RTM Protocol's acceptability and adaptability during training and practice through case statistics, satisfaction surveying of MH practitioners and clients, and focus-group interviews with MH practitioners.

Objective 1: *To analyse the acceptability of the RTM Protocol among MH professionals and persons with trauma-related MH conditions)*

Objective 2: *To analyse the adaptability (Usability of the Ukrainian language versions) of the RTM Protocol*

Data will be collected, pseudonymised in Ukraine by implementing partners - the Centre of Mental Health and Rehabilitation "Forest Glade" of the Ministry of Health of Ukraine (RCFG) and the National Psychological Association of Ukraine (NPAU), and transferred in fully anonymised, aggregated form to the University of Luxembourg for analysis. Findings will inform humanitarian response policy and sustainable capacity-building for evidence-based PTSD treatment in low-resource, conflict settings.

SECTION 3: AIM OF EACH OF THE STUDIES

Study No.	Aim	Study will involve: Please tick all appropriate boxes
Study 1: The RTM Protocol effectiveness study	To compare the effectiveness of the RTM Protocol for the treatment of PTSD with other evidenced-based trauma-focused therapies (TF-CBT, EMDR and medication) in different settings of MH care accustomed for Ukraine (inpatient and outpatient hospital care for war veterans and psychotherapy for civil trauma survivors).	 Human participants  Vulnerable population  Human biological material  Pre-collected biological material  Personal data  Pre-collected personal data  risks on the environment  risks on the society

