Expected duration of procedure:	Data collection will occur at baseline (diagnostic session), 1 month after complete treatment application, in 6 months (follow-up booster session), and in 12 months (second follow-up booster session) and will take approximately 15 min each, 45 min per person.
Data Collection:	
Paper questionnaires, digital entry; no audio/video.
 
Data on age, gender, veteran and IDP statuses, residency, type of trauma, medical diagnosis and symptoms, scores from PCL-5 (for PTSD), PHQ-9 (for depression), GAD-7 (for anxiety) diagnostic scales will be collected from printed questionnaire sheets filled in by participants.
 
PTSD diagnosis will be collected from medical records.
 
Names, email-address, phone number will be collected from printed informed consent.
 
Data transfer. Aggregated, fully anonymised raw data will be shared by implementing partners' coordinators through Zenodo under closed access and using the EUSurvey Platform (an online survey-management

	
system developed by the European Commission) only with PI [name].

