
Human participants are involved in the study with potential risk related to
 
 Physical harm  Psychological harm  Invasion of privacy  Social and economic harm  Other
	
Personal data will be collected (see data collection section).
 
Data collection measures. Implementing partners' coordinators will collect data using printed versions of questionnaires (which will be destroyed after data e-input and prior this time they will be stored in a secure storage cabinet). Mental health professionals involved in the research will collect data on clients (people with PTSD) using clinical scales which will be destroyed after data e-input and before it will be stored in a secure storage cabinet.
 
Data Storage measures. The e-data will be stored on encrypted hard drives and will be accessible only to implementing partners' coordinators. They will create password-protected access to the data with the help of the organisations' IT departments.
 
Data Pseudonymization measures. The data will be pseudonymized by the implementing partners' coordinators and professionals involved in the research for the purpose of follow-up assessments using European Data Protection Board Guidelines on Pseudonymisation, 2025.
 
Usage and storage of personal data will fully comply with Ukrainian legislation, the Civil Code of Ukraine, and the Law of Ukraine on the Protection of Personal Data.
 
No mentioned non-anonymized personal data will be used for the research purposes, transferred or processed in Luxembourg.

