
Human participants are involved in the study with potential risk related to
 
 Physical harm
 
 Psychological harm
 
 Invasion of privacy
 
 Social and economic harm
 
 Other
	
Personal data will be collected (see data collection section).
 
Data collection measures. Implementing partners' coordinators will collect data using printed versions of questionnaires (which will be destroyed after data e-input and prior this time they will be stored in a secure storage cabinet) and focus-group interviews audio-recordings with following transcription. Mental health professionals involved in the research will collect data on clients (people with PTSD) using printed versions questionnaires which will be destroyed after data e-input and before it will be stored in a secure storage cabinet.
 
Data Storage measures. The e-data will be stored on encrypted hard drives and will be accessible only to implementing partners' coordinators. They will create password-protected access to the data with the help of the organisations' IT departments.
 
Data Pseudonymization measures. The data will be anonymized by the implementing partners' coordinators.
 
Usage and storage of personal data will fully comply with Ukrainian legislation, the Civil Code of Ukraine, and the Law of Ukraine on the Protection of Personal Data.
 
No mentioned non-anonymized personal data will be used for the research purposes, transferred or processed in Luxembourg.

Are there any specific risks to the human participants involved, if any.
	
There are no anticipated specific risks for the human participants.

SECTION 6: DATA PROTECTION

Study 1: The RTM Protocol Effectiveness Study

The Project PI will have access only to aggregated, anonymised data. The implementing partners' coordinators and professionals involved in the research will collect, pseudonymise (for the purpose of follow-up assessment in two weeks, six months, and one year), and anonymise the clients' data. Implementing partners' coordinators will aggregate the data and input it on the EU Survey Platform (an online survey-management system developed by the European Commission) to transfer it to Luxembourg. The transferred data will be stored on the University of Luxembourg-protected server ATLAS for up to 10 years.

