The Project PI will have access only to aggregated anonymised data (professionals-participants' occupation, place of work, duration of professional experience, trauma-centred methods used, data from satisfaction surveying, Intervention Usability Scale and focus-group interview etc.) Implementing partners' coordinators will collect, anonymise, aggregate the data and input it on the EUSurvey Platform (an online survey-management system developed by the European Commission) to transfer it to Luxembourg. Focus-group interview transcripts' transfer to Luxembourg will be done through Zenodo under closed access. The transferred data will be stored on the University of Luxembourg-protected server ATLAS for up to 10 years.

Comments on the possible misuse of the research:

The Lux4UA project is designed exclusively to evaluate the effectiveness and feasibility of the RTM Protocol. It does not aim to collect prevalence data, epidemiological statistics, or any form of population-level surveillance. All data are collected solely for the purpose of assessing therapeutic outcomes and implementation feasibility within predefined clinical settings.

No new diagnostic tools are being developed, and no data will be used to infer broader mental health trends or conditions across populations. The study samples are limited, purposive, and context-specific, selected based on clinical availability. Therefore, the findings cannot be extrapolated to estimate prevalence or inform policy beyond the scope of treatment evaluation.

Furthermore, the project does not involve any form of geolocation, behavioral tracking, or longitudinal profiling beyond anonymized follow-up assessments. All data are pseudonymized and aggregated before analysis, and no individual-level identifiers are retained or transferred.

Given the sensitive context of war and displacement, we acknowledge the theoretical risk of misinterpretation or misuse of mental health data. To mitigate this, the project adheres strictly to ethical guidelines from EFPA, CIOMS, and the IASC, and all implementing partners operate under national ethical oversight. The research outputs will be framed explicitly within humanitarian and clinical care contexts, avoiding any language or framing that could be construed as diagnostic surveillance or military profiling.

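### Does the promise to aggregate Study 1 data before transfer rule out the planned repeated-measures analysis?

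*Protocol*

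**What the plan says.** The transfer of Study 1 data is described in several places, and the wording varies.

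- Section 2 (short summary): data are "transferred in fully anonymised, aggregated form to the University of Luxembourg for analysis".
- Section 6, Study 1: "The Project PI will have access only to aggregated, anonymised data", and the partners' "coordinators will aggregate the data and input it on the EU Survey Platform".
- Section 6, comments on possible misuse: "All data are pseudonymized and aggregated before analysis, and no individual-level identifiers are retained or transferred".
- Section 4, Study 1, Data transfer, and again under Data access, Data sharing: "Aggregated, fully anonymised raw data will be shared by implementing partners".
- Section 5, Study 1: "No mentioned non-anonymized personal data will be used for the research purposes, transferred or processed in Luxembourg".

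The analysis is set in Section 4, Study 1, Methodology: "Primary and Secondary Outcome Analysis: mixed-effects repeated measures ANOVA", with missing data handled by "multiple imputation or maximum likelihood estimation under MAR assumption".

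Section 6, Study 1, also describes the participant ID (PID). It carries codes for arm and setting plus a sequence number, it is written on every follow-up document, and its stated purpose is to link repeated assessments. A key held at each site connects it to contact details.

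**The concern.** *Aggregated* is never defined. A statistician's first reading is group summaries: a table of means and SDs by arm, setting and visit. A repeated-measures mixed model needs each person's scores linked across visits. Imputation or likelihood methods under missing at random need to know which earlier scores belong to the people who later drop out. A table of summaries gives neither.

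The analysis is placed in Luxembourg, and the sites' electronic data are open only to the coordinators. If summaries were sent, the primary analysis could not be done as planned, and the protocol describes no site-level analysis as a substitute.

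The sentence in the comments on misuse also says that identifiers are not retained. The Data storage table, however, keeps identifying data until 5 years after the project ends.

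**Working it through.** **What group summaries would cost**

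Inputs: 3 settings, 2 arms and 20 participants per sample (Section 6, Study 1); 4 assessments, namely baseline and three follow-ups (Section 4, Study 1); SD 3.0 for PCL-5 and 20% dropout (Section 4, Target sample size). The first follow-up is put at 1 month in Section 4 and at 2 weeks in Section 6, but the count of four is the same either way.

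1. The plan's own total: 3 × 2 = 6 samples, and 6 × 20 = 120 participants. This reproduces.
2. Summary cells per scale: 6 × 4 = 24, in place of 120 × 4 = 480 person-visit values.
3. Within-person covariance matrix for 4 visits: 4 × 5 / 2 = 10 distinct terms, made up of 4 variances and 6 covariances. Visit SDs supply the 4 variances and none of the 6 covariances.
4. Incomplete follow-up: 0.20 × 120 = 24 participants whose earlier scores could not be picked out.
5. Effect on precision for a between-arm difference in change, with 3 × 20 = 60 per arm and within-person correlation r: SE = √(2 × 2 × 3.0² × (1 − r) / 60) = √(0.6 × (1 − r)). The protocol gives no r, so a range is assumed: 0.775 at r = 0, 0.548 at r = 0.5 and 0.245 at r = 0.9. Summaries would leave this roughly threefold range unresolved.

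The loss would be serious, but only if summaries are what the protocol means.

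**Which reading the text supports**

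1. The two places that specify the transfer itself (Section 4, Data transfer; Data access, Data sharing) put *aggregated* and *raw* in one phrase. Means and SDs are not raw data. Anonymised records pooled across sites are.
2. The sentence in the comments on misuse pairs aggregation with pseudonymisation. A pseudonym belongs to a person's record, not to a cell mean.
3. Section 6, Study 2, calls the professionals' data aggregated too, including occupation, usability scores and focus-group material, the last of which is sent as transcripts. Section 4, Study 2, Methodology plans Spearman correlations between usability scores and satisfaction or case outcomes. A rank correlation needs paired individual values, so in that study the word has to mean collected together.
4. The Data storage table names the analysis material as Excel files exported from EUSurvey. No section mentions a table of means or SDs as something to be sent.

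**Whether the links survive**

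Visits, arm and setting are linked in the site data from which the transfer file is made. A file with one row per participant, an arm column, a setting column and one column per visit and scale holds everything the model needs, and it does so without the PID. Under this reading the loss is zero.

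**The case for a change.** The strongest case for a change has three parts.

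First, Section 2 and Section 6, Study 1, say aggregated without the word raw, and Section 6 limits the PI to such data. A cautious coordinator could take this literally.

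Second, the PID is what links the visits. Its key leads to contact details, Section 5 bars non-anonymised personal data from transfer, and the comments on misuse exclude individual identifiers. The PID may therefore have to stay behind, and nothing is named to replace it.

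Third, this is a promise about data access, which a statistical analysis plan should not quietly widen.

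It stands that the word is undefined and that a literal summary reading would not fit the analysis. The second part carries less weight. Whether a PID without its key counts as personal data is a classification the protocol leaves to guidelines, and it need not be settled here. The exclusions cover identifiers and identifiable data, not anonymised score rows, so a wide row needs no PID. On the third part, anonymised rows stay within a promise that already speaks of raw data, so access is not widened.

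A wrong file would also show itself at once (24 cells per scale instead of 120 records), and it could be sent again while the sites hold their electronic records and key.

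The clash over retained identifiers is real on the page. The sentence makes sense if it describes the data sent for analysis, with the key list staying at the sites as the Data storage table says. It is a slip in data-protection wording and touches no estimate.

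**Conclusion.** No change to the plan is needed. Pooled, anonymised participant rows are the better-supported meaning of *aggregated*, and under that meaning the planned model and missing-data methods run with no loss. The 24 cells, 6 missing covariances and 24 unidentifiable dropouts arise only under the weaker reading.

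This rests on two assumptions that the protocol does not spell out: each site joins a participant's visits before removing the PID, and arm and setting stay in the file as columns. Both are ordinary practice, since the trial exists to compare arms and settings over time and the PID was set up to make the links. Row unit, key and columns are the sort of detail commonly left to a data-management document or an analysis plan. A clearer word than *aggregated* would be welcome if the text is revised for other reasons, but the analysis does not depend on it.
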